- Grade ≥ 3 total bilirubin or hepatic transaminase (aspartate aminotransferase [AST] and alanine aminotransferase [ALT]) elevations that return to ≤ Grade 1 (if normal at study entry) or ≤ baseline values within 7 days of interrupting study drug;
- Note: Allergic reactions that necessitate discontinuation of study drug will not be considered a DLT;
- Grade ≥ 3 symptomatic fasting hyperglycemia (e.g., dehydration or acidosis requiring hospitalization);
- Grade ≥ 4 fasting hypercholesterolemia or triglyceridemia for ≥ 14 days despite intervention with a lipid-lowering agent:
- Grade ≥ 4 thrombocytopenia;
- Grade 3 thrombocytopenia that lasts ≥ 7 days or is associated with clinically significant bleeding;
- Grade ≥ 4 neutropenia (absolute neutrophil count < 500/µL) lasting ≥ 7 days or accompanied by fever (oral or tympanic temperature ≥ 38.0°C [100°F]);
- Grade ≥ 3 total bilirubin or hepatic transaminase (ALT or AST) elevations that do not return to ≤ Grade 1 (if normal at study entry) or ≤ baseline values within 7 days of interrupting study drug;
- For patients with Gilbert's disease and with Grade 2 bilirubin at baseline, total bilirubin $\ge 10 \text{ x}$ the upper limit of normal (ULN) will be considered a DLT:
- Bradycardia Grade ≥ 2;
- Myocardial ischemia Grade ≥ 2;
- Mucositis/stomatitis Grade 3 not responding to standard-of-care therapy or Grade 4;
- Decrease in left ventricular ejection fraction (LVEF) to ≤ 45%;
- Increase of QTc to ≥ 500 msec or by 60 msec;
- Pneumonitis Grade ≥ 2.

After determination of the MTD, patients continue to receive their protocolassigned dose level of GDC-0084 until progression of their disease or an unacceptable toxicity, whichever occurs first.

Sponsor: Kazia Therapeutics Limited Version: Amendment 4 Date: 31 Mar 2020

Protocol Number: NVGN-0084-201

IND Number: 112,608

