Protocol Number: NVGN-0084-201 Version: Amendment 4 IND Number: 112,608

Dose-Escalation Rules

Dose-escalation will occur in Stage 1:

The initial dose (Dose Level 0) for QD MTD determination in will be 60 mg. Dose levels will increase in 15 mg steps:

- The dose-escalation portion of the study (Stage 1) will use a "3 + 3" design to assess the safety, tolerability, and PK of GDC 0084 administered orally in 28-day cycles:
- Each dose cohort will initially enroll 3 patients. If none of these patients experiences a DLT within the DLT assessment period (Day 1 - 28), escalation will proceed to the next higher dose level by opening the next higher dose cohort with newly recruited patients;
- If 1 patient experiences a DLT, the cohort will be expanded until a second patient experiences a DLT or to a maximum of 6 patients. When a second patient has a DLT, the MTD is determined as 1 dose level below the current dose level; i.e. the highest dose level at which less than 1/3 of patients (e.g. 1 of 6) experiences a DLT will be declared the MTD.
- If 2 or more patients experience a DLT at Dose Level 0, the MTD will be declared at 45 mg, which was the MTD established in the previous phase I study in patients with advanced glioma with a QD dosing schedule.

On the basis of the review of real-time safety data and available preliminary PK data from this study with GDC-0084, dose-escalation may be halted or modified by the sponsor as deemed appropriate.

Decisions regarding dose-escalation and selection will be made by a CRC including the medical monitor, recruiting Investigators, sponsor representative and any other relevant and necessary expert on as needs basis, according to the CRC charter.

Definition of Dose Limiting Toxicity

All AEs, including DLTs, will be reported, with severity assessed according to National Cancer Institute (NCI) Common Terminology Criteria for Adverse Events (CTCAE), version 4.03. In case a patient experiences one of the below, study participation will be terminated for this patient and the EoT visit should be performed.

For dose-escalation purposes, DLT assessments will be performed by the sponsor in consultation with the Investigators during the CRC meetings.

A DLT is defined as any one of the following toxicities occurring within the DLT assessment window (Cycle 1, Days 1 - 28) and assessed by the Investigator to be probably or possibly related to GDC-0084:

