- Grade ≥ 3 non-hematologic or non-hepatic toxicity that is not related to hyperglycemia or hyperlipidemia or mucositis/stomatitis and is not due to disease progression or another clearly identifiable cause, excluding the following:
 - Alopecia of any grade;
 - Grade 3 fever or Grade 4 fever < 5 days duration;
 - Grade 3 infection < 5 days duration or that responds to treatment;
 - Grade 3 weight gain or loss;
 - Grade 3 diarrhea lasting less than 5 days or that responds to standard-of-care therapy including hospitalization;
 - Grade 3 nausea or vomiting, in the absence of premedication, that lasts for less than 48 hours or responds to standard-of-care therapy:
 - Grade 3 or asymptomatic Grade 4 electrolyte imbalance that resolves or improves within 7 days with or without medical intervention, including hospitalization;
 - Grade 3 or 4 serum amylase or lipase or creatine phosphokinase laboratory abnormality that is asymptomatic (without other laboratory evidence suggestive of pancreatitis, rhabdomyolysis, or other major organ dysfunction) and returns to baseline within 7 days of interrupting study drug;

Version: Amendment 4 Date: 31 Mar 2020

Protocol Number: NVGN-0084-201 IND Number: 112.608

o Grade ≥ 3 total bilirubin or hepatic transaminase (aspartate aminotransferase [AST] and alanine aminotransferase [ALT]) elevations that return to ≤ Grade 1 (if normal at study entry) or ≤ baseline values within 7 days of interrupting study drug:

- Note: Allergic reactions that necessitate discontinuation of study drug will not be considered a DLT:
- Grade ≥ 3 symptomatic fasting hyperglycemia (e.g., dehydration or acidosis requiring hospitalization):
- Grade ≥ 4 fasting hypercholesterolemia or triglyceridemia for ≥ 14 days despite intervention with a lipid-lowering agent;
- Grade ≥ 4 thrombocytopenia;
- Grade 3 thrombocytopenia that lasts ≥ 7 days or is associated with clinically significant
- Grade ≥ 4 neutropenia (absolute neutrophil count < 500/µL) lasting ≥ 7 days or accompanied by fever (oral or tympanic temperature ≥ 38.0°C [100°F]);
- Grade ≥ 3 total bilirubin or hepatic transaminase (ALT or AST) elevations that do not return to ≤ Grade 1 (if normal at study entry) or ≤ baseline values within 7 days of interrupting study drug:
- For patients with Gilbert's disease and with Grade 2 bilirubin at baseline, total bilirubin ≥ 10 x upper limit of normal (ULN) will be considered a DLT;
- Bradycardia Grade ≥ 2;
- Myocardial ischemia Grade ≥ 2;

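### Read literally, the first DLT bullet makes related Grade 3 or higher cytopenias DLTs, overriding the narrower platelet and neutrophil limits unless another cause is clear

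*Combined protocol and SAP*

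**What the plan says.** Section 3.7.1 (Definition of Dose Limiting Toxicity) gives a bulleted list, repeated in the synopsis. The bullets are alternatives: "A DLT is defined as any one of the following toxicities occurring within the DLT assessment window". An event must also be judged possibly or probably related to GDC-0084.

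- **First bullet.** It covers "Grade ≥ 3 non-hematologic or non-hepatic toxicity that is not related to hyperglycemia or hyperlipidemia or mucositis/stomatitis". It leaves out events explained by progression or by another clear cause. A list of exclusions follows, and none of them concerns a cytopenia. One concerns bilirubin and transaminase "elevations that return to ≤ Grade 1 (if normal at study entry) or ≤ baseline values within 7 days of interrupting study drug".
- **Platelet bullets.** Grade 4 counts at any duration. Below that, the rule is "Grade 3 thrombocytopenia that lasts ≥ 7 days or is associated with clinically significant bleeding".
- **Neutrophil bullet.** Only Grade 4 or higher counts, and only when "lasting ≥ 7 days or accompanied by fever".
- **Hepatic bullet.** A separate bullet covers Grade 3 or higher bilirubin or transaminase elevations that have not recovered within 7 days of interruption.

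The escalation rule in the same section is: "When a second patient has a DLT, the MTD is determined as 1 dose level below the current dose level". Two DLTs at 60 mg return the MTD to 45 mg. Section 4.5.1 makes the occurrence of DLTs the primary endpoint. Section 4.11.2 refers back to 3.7.1 for the details. Section 6.3.5 treats low platelets as a DLT criterion in its own right.

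**The concern.** The conjunction in the first bullet conflicts with the hematologic bullets. With *or*, an event escapes the opening words only if it is both hematologic and hepatic, so the phrase filters out almost nothing. A brief Grade 3 platelet fall without bleeding then satisfies the general bullet, although the platelet bullet was evidently written to spare it.

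The classification matters because a 3+3 cohort has at most six patients and turns on the second DLT. One reclassified event can set the MTD a level lower, or return it to the phase 1 value that Stage 1 was designed to try to exceed. It also matters for the patient. Section 3.7.1 says that on one of the listed toxicities "study participation will be terminated for this patient and the EoT visit should be performed", and the Duration of Therapy section lists a Cycle 1 DLT in Stage 1 as a reason to end treatment. Section 3.7.1 does allow continuation after a reversible event if the Investigator and medical monitor agree.

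**Working it through.** **1. Logic of the opening phrase.** Let H mean hematologic and L mean hepatic.

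| Event | Literal: (not H) or (not L) | *Neither*: (not H) and (not L) |
|---|---|---|
| Cytopenia (H, not L) | true | false |
| Hepatic event (not H, L) | true | false |
| Rash (neither) | true | true |

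**2. Effect on related Cycle 1 events with no clear alternative cause.**

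| Event | Platelet or neutrophil bullet met? | DLT, literal | DLT, *neither* |
|---|---|---|---|
| Grade 3 platelets, 3 days, no bleeding | no | yes | no |
| Grade 3 platelets, 8 days | yes | yes | yes |
| Grade 4 platelets | yes | yes | yes |
| Grade 4 neutropenia, under 7 days, no fever | no | yes | no |
| Grade 4 neutropenia, 7 days or more, or febrile | yes | yes | yes |
| Grade 3 neutropenia, with or without fever | no | yes | no |
| Grade 3 or higher anemia or lymphopenia | no such bullet | yes | no |

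Bilirubin and transaminase elevations that lead to interruption classify the same way under both readings. If they recover within 7 days they are not DLTs, and otherwise they are.

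**3. Where the narrower limits still work.** The alternative-cause exemption belongs to the first bullet only. Section 5.8 defines *possibly related* so that another explanation can coexist. Take a possibly related cytopenia with a clear competing cause, such as prior temozolomide, which section 4.10.5 says often causes lymphopenia. The first bullet does not apply. Grade 3 platelets for 3 days without bleeding is then not a DLT, and for 8 days it is. So the limits are overridden for one class of event and still decide another.

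**4. Evidence on intent.** For *neither*: the platelet and neutrophil bullets would have little purpose otherwise, and section 6.3.5 lists low platelets as a separate criterion. For *or*: the bilirubin/transaminase exclusion nested under the first bullet is needed only if hepatic events fall inside that bullet. Section 4.11.2 adds nothing, and the Cohort Review Committee (CRC) charter is not among the documents.

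**5. Size, from the documents.** The Risk/Benefit Analysis reports 47 phase 1 patients at 2 to 65 mg. The most common related Grade 3 events were hyperglycemia at 8.5% (4/47 = 8.51%) and mucositis at 6.4% (3/47 = 6.38%). On that description no other single related Grade 3 term should exceed 3/47. This does not cap cytopenias taken together, Grade 4 events, or the rate at 60 mg and above. That section names no cytopenia among the frequent events or the DLTs.

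**6. Size, by illustration.** The rates here are assumed, because the documents give none. Let b be the DLT probability from all other criteria, and c the probability of a cytopenia that counts only under the literal reading, independent of b. Then p = 1 − (1 − b)(1 − c). The chance of escalating past a dose, with 0 of 3 or 1 of 6 DLTs, is (1 − p)³ + 3p(1 − p)² × (1 − p)³.

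| b | c = 0 | c = 5% | c = 10% | c = 20% |
|---|---|---|---|---|
| 10% | 0.906 | 0.824 | 0.730 | 0.536 |
| 20% | 0.709 | 0.622 | 0.536 | 0.378 |

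For example, b = 10% and c = 5% give p = 1 − 0.90 × 0.95 = 0.145, and 0.625 + 0.199 = 0.824. The c = 0 column is the *neither* reading.

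**The case against.** The best defense is that the meaning can be recovered from the text. The same sentence uses *or* for *nor* when it sets aside hyperglycemia, hyperlipidemia and mucositis, and each of those has its own later bullet, as platelets, neutrophils and bilirubin/transaminases do. Nor do sites apply the text alone: "DLT assessments will be performed by the sponsor in consultation with the Investigators during the CRC meetings". The likely effect is small, and the literal error is conservative. The correction also narrows the definition, because under *neither* no bullet covers Grade 3 neutropenia with fever, anemia or lymphopenia.

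Most of this stands. It makes *neither* the likely intent and limits the practical risk. It does not settle the text, because the nested hepatic exclusion points the other way and no supplied section resolves the conflict. The coverage gap is a reason to settle those events in the same amendment.

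One smaller point also stands. Both hepatic provisions depend on recovery after interruption, so an elevation that settles while dosing continues is not clearly handled by either.

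A reader might infer that the platelet and neutrophil limits have no effect at all. They do have an effect wherever a possibly related cytopenia has another clear cause. A reader might also infer that short cytopenias have been counted as DLTs, or that escalation is unsafe. No document shows a call made on the literal reading, and counting more events as DLTs favors stopping early.

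**Conclusion.** The definition is wrong as written and should be corrected. Read literally, it makes a DLT of any related Grade 3 or higher cytopenia without a clear alternative cause, and for those events it overrides the stated platelet and neutrophil limits. The effect is probably small. That judgment rests on the phase 1 summary, which is pooled over doses mostly below those in this study, and on the expectation that the CRC applies the likely intent. The escalation probabilities show sensitivity only; they depend on assumed rates and independence and are not estimates for this trial. The case for correction is that this list is the stated rule for the primary endpoint and for the MTD, and it should have one meaning.

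**What to change.** In the synopsis and in section 3.7.1:

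- Open the first bullet with *Grade ≥ 3 toxicity that is neither hematologic nor a bilirubin/transaminase elevation*, and keep the rest of the sentence. Naming these laboratory elevations, not hepatic toxicity in general, keeps other Grade 3 or higher hepatic events within the general bullet; no other bullet covers them.
- Delete the bilirubin/transaminase exclusion nested under that bullet. The separate bullet for elevations that do not recover within 7 days then governs. A few words there could say what applies when dosing is not interrupted.
- In the same amendment, state whether Grade 3 neutropenia with fever, Grade 3 or higher anemia and Grade 3 or higher lymphopenia are DLTs. This is a clinical choice.
- Confirm that Stage 1 DLT calls already made used the corrected reading. If any did not, the CRC should revisit that cohort's decision.

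The cost is a small wording amendment with IRB approval under section 10.4, a check of past calls, and a narrower literal DLT definition unless the sponsor adds the uncovered cytopenias.

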4.6.8 Safety Laboratory Assessments

Blood samples of approximately 10 mL per assessment of hematological and serum chemistry parameters will be collected and processed in accordance with the laboratory procedures.

All hematology and serum chemistry samples will be submitted by the Investigator to the certified laboratory for analysis. Blood samples for hematology and serum chemistry will be prepared using standard procedures. Laboratory results should be reviewed by the Principal Investigator or another qualified study staff member as soon as received.

Safety laboratory panels are defined as follows:

Protocol Number: NVGN-0084-201 Version: Amendment 4 IND Number: 112.608 Date: 31 Mar 2020

Hematology and Coagulation: red blood cell count (RBC), hemoglobin, hematocrit, reticulocyte count, WBC with differential (neutrophils, bands, eosinophils, basophils, lymphocytes, monocytes, and other cells), platelet count aPTT, PT, and INR;

Serum chemistry: blood urea nitrogen (BUN) or urea, creatinine, sodium, chloride, potassium, magnesium, bicarbonate, calcium, phosphorus, total protein, albumin, alkaline phosphatase, fasting glucose, total bilirubin, direct and indirect bilirubin, lactate dehydrogenase (LDH), cholesterol, uric acid, triglyceride levels, gamma glutamyl transferase (GGT), AST, and ALT.

Abnormalities in clinical laboratory tests that are considered clinically significant by the Investigator will be recorded on the laboratory Case Report Form (CRF) page. If abnormal laboratory results are also considered an AE, then a corresponding AE CRF will also be completed. If values after the first dose meet criteria defining them as serious, they must be reported as SAEs.

Unscheduled and repeat laboratory tests may be performed by the laboratory to allow a short as possible turnaround time for rapid clinical management of the patient, if necessary. A Laboratory Manual with instructions on specimen collection, processing, storing, and shipping will be in place for all participating sites.

4.6.9 **Pregnancy Test**

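### The DLT definition tests amylase, lipase and creatine phosphokinase against baseline, but no baseline or routine measurement of them is scheduled, so asymptomatic elevations would be missed and the exclusion cannot be applied as written

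*Combined protocol and SAP*

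**What the plan says.** The DLT definition in 3.7.1 (repeated in the Synopsis) opens with a broad criterion, "Grade ≥ 3 non-hematologic or non-hepatic toxicity that is not related to hyperglycemia or hyperlipidemia or mucositis/stomatitis", followed by a list of exclusions. One exclusion covers a "Grade 3 or 4 serum amylase or lipase or creatine phosphokinase laboratory abnormality that is asymptomatic", meaning without other laboratory signs of pancreatitis, rhabdomyolysis or other major organ dysfunction, "and returns to baseline within 7 days of interrupting study drug". The event must fall in Cycle 1, Days 1 to 28, and be judged possibly or probably related to GDC-0084.

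Section 4.6.8 introduces the tests with "Safety laboratory panels are defined as follows" and then itemises them. The chemistry list begins "Serum chemistry: blood urea nitrogen (BUN) or urea, creatinine, sodium, chloride, potassium, magnesium, bicarbonate, calcium, phosphorus, total protein, albumin, alkaline phosphatase" and continues through fasting glucose, bilirubin, LDH, cholesterol, uric acid, triglycerides, GGT, AST and ALT. Amylase, lipase and creatine phosphokinase do not appear. Table 1 and its footnotes have no separate line for them.

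Table 1 schedules chemistry at Screening, C1D1, C2D1 and every 4 weeks thereafter. Section 4.9.1 asks for laboratory results in the 48 hours before each cycle. Section 6.3.5 defines the laboratory baseline as the last value before the first dose.

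**The concern.** Because the enzyme clause is an exclusion, an abnormality that fails it falls back under the parent criterion and is a DLT if related. A Grade 3 or 4 elevation that causes no symptoms but does not settle in time is therefore a DLT, and only a blood test can reveal it. The protocol schedules no such test. Nor can an unseen elevation prompt the drug interruption from which the 7 days are counted.

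DLTs are the primary endpoint (4.5.1), and their count drives the 3+3 rule, under which one event among three patients changes the next step. Escalation starts at 60 mg, above the 45 mg MTD of the earlier phase 1 study, so complete ascertainment of DLTs matters here.

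The gap looks like an omission. The other laboratory-based DLT criteria rest on analytes that are in the panel: platelets, neutrophils, bilirubin, transaminases, fasting glucose, lipids and electrolytes. Where the protocol wants off-panel tests it names them: troponin T and B-type natriuretic peptide in 4.6.4, and creatine kinase in the liver-injury work-up of 5.5.1.

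**Working it through.** The plan states no figure to reproduce. The main check sets the rule beside the measurements.

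| What the exclusion in 3.7.1 needs | What the protocol schedules |
|---|---|
| A Grade 3 or 4 value of one of the three analytes is seen | No routine measurement (4.6.8, Table 1) |
| A pre-dose value to return to | Baseline is defined in 6.3.5, but no pre-dose value is scheduled for these analytes |
| A repeat value at 7 days or less after interruption | No chemistry draw between C1D1 and C2D1 |

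Three kinds of event then behave differently.

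1. Symptomatic, or with other laboratory evidence of organ dysfunction. The exclusion does not apply, and a related Grade 3 or higher event is a DLT with no baseline value needed. It can be found clinically.
2. Asymptomatic and not tested. It is not seen or counted. If it would have failed the exclusion, the DLT count is one too low.
3. Asymptomatic but found by an unscheduled test. If it is still Grade 3 or higher after 7 days, it can usually be judged a DLT without an exact baseline. If it has fallen to, say, Grade 1, the answer depends on whether the patient started at Grade 0 or Grade 1, which is unknown. One assessor may hold that return to baseline is not shown and count a DLT. Another may presume that it is shown and exclude the event.

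To illustrate the size of the second case, suppose a fraction q of patients have other DLTs and, independently, a fraction u have an enzyme DLT that goes undetected. Both rates are assumed, because the documents give neither. A level is passed with 0 of 3 DLTs, or with 1 of 3 followed by 0 of 3:

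E(p) = (1 − p)^3 + 3p(1 − p)^2 × (1 − p)^3 = (1 − p)^3 + 3p(1 − p)^5

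If the enzyme DLTs are missed, p = q. If all are detected, p = 1 − (1 − q)(1 − u).

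Example with q = 0.20 and u = 0.05:
- Missed: 0.8^3 + 0.6 × 0.8^5 = 0.512 + 0.197 = 0.709.
- Detected: p = 1 − 0.80 × 0.95 = 0.24, so 0.76^3 + 0.72 × 0.76^5 = 0.439 + 0.183 = 0.622.
- Difference: 0.087.

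| q | E if missed | E if detected, u = 2% | u = 5% | u = 10% |
|---|---|---|---|---|
| 10% | 0.906 | 0.875 (+0.031) | 0.824 (+0.082) | 0.730 (+0.176) |
| 20% | 0.709 | 0.674 (+0.035) | 0.622 (+0.087) | 0.536 (+0.173) |
| 30% | 0.494 | 0.466 (+0.028) | 0.425 (+0.069) | 0.360 (+0.134) |

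The brackets show how far the chance of passing the level is overstated when the events are missed.

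**The case against.** A reader might infer that these DLTs can be neither detected nor adjudicated. The documents do not support that. Sections 4.6.8 and 4.6.11 allow unscheduled and additional tests, 4.10.3 asks for close clinical and laboratory follow-up of gastrointestinal effects, and 5.5.1 orders creatine kinase in a suspected liver-injury case. Symptomatic events need no baseline to count. This part of the objection stands and confines the problem to asymptomatic elevations. It does not remove the problem, because leave to test on suspicion does not find an event that raises no suspicion, and a later test cannot supply a pre-dose value.

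A reader might also infer a uniform bias toward escalation. That holds only for missed events. Where an event is found and return to baseline cannot be shown, the exclusion may be held to fail, which adds a DLT and works against escalation.

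The assumed rates can fairly be called unanchored. The phase 1 summary in the Risk/Benefit Analysis section covers 47 patients and names no amylase, lipase or creatine phosphokinase event, though it does not say whether these were measured. The table also compares missing every such event with detecting every one, and routine assays at the existing visits would not achieve the latter. Both criticisms stand, so the table is an illustration and not an estimate.

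Finally, the Laboratory Manual might add the assays. Section 4.6.8 describes it as covering how specimens are collected, processed, stored and shipped, so this cannot be presumed.

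**Conclusion.** The mismatch between 3.7.1 and 4.6.8 is real and can be read directly from the text. Followed as written, the protocol takes no baseline or routine value of the three analytes. Scheduled testing would miss asymptomatic Grade 3 or 4 elevations, which can only lower the DLT count. For those found by an unscheduled test, the return-to-baseline condition cannot be applied as written, and the classification could go either way. The point does not extend to symptomatic events.

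The size cannot be established from the documents. Under assumed undetected rates of 2%, 5% and 10%, with other DLTs in 10% to 30% of patients and independence between the two, the chance of escalating past a level would be overstated by about 3, 7 to 9, and 13 to 18 percentage points, if all such events would otherwise be detected. The planned sample size is unaffected. Because the primary endpoint is involved and the correction is cheap, it should be made.

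**What to change.** Reconcile 3.7.1 (and the matching Synopsis text) with 4.6.8. The simplest way is to add amylase, lipase and creatine phosphokinase to the serum chemistry list, run on the sample already drawn at Screening, C1D1 and later visits, and to have the DLT rule refer to the baseline definition already in 6.3.5. No new definition is needed. If the sponsor prefers to change the exclusion instead, its clinical content is the sponsor's decision. Either way the two sections must agree.

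The cost is a small laboratory charge, a line in 4.6.8 and in the Laboratory Manual, and some incidental abnormalities to review. No visit, dose or sample size changes.

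The change has a limit. It supplies a baseline and a value at about the end of Cycle 1: C2D1 is nominally Day 29, just outside the DLT window, although the check in the 48 hours before the cycle may fall inside it. With no chemistry draw scheduled between C1D1 and C2D1, the 7-day return check would still depend on unscheduled tests, and the revised text should say so.

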Abnormal values in AST and/or ALT concurrent with abnormal elevations in total bilirubin that meet the criteria outlined below in the absence of other causes of liver injury are considered potential cases of drug-induced liver injury (potential Hy's Law cases) and should always be considered important medical events.

The threshold of laboratory abnormalities for a potential case of drug-induced liver injury depends on the patient's individual baseline values and underlying conditions. Patients who present with the following laboratory abnormalities should be evaluated further to definitively determine the etiology of the abnormal laboratory values:

- Patients with AST or ALT and total bilirubin baseline values within the normal range who subsequently present with AST or ALT ≥ 3 x ULN concurrent with a total bilirubin ≥ 2 x ULN with no evidence of hemolysis and an alkaline phosphatase $\leq 2 \times \text{ULN}$ or not available;
- For patients with preexisting ALT OR AST OR total bilirubin values above the upper limit of normal, the following threshold values should be used in the definition mentioned above:
- For patients with pre-existing AST or ALT baseline values above the normal range: AST or ALT \geq 2 x the baseline values and \geq 3 x ULN, or \geq 8 x ULN (whichever is smaller);
- For patients with pre-existing values of total bilirubin above the normal range: Total bilirubin increased by one time the ULN $or \ge 3$ x the lower limit of normal (whichever is smaller).

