If able to do so, the patient should return to the investigational site and be evaluated as soon as possible, preferably within 48 hours from awareness of the abnormal results. This evaluation should include laboratory tests, detailed history and physical assessment. For oncology studies, the possibility of hepatic neoplasia (primary or secondary) should be considered. In addition to repeating AST and ALT, laboratory tests should include albumin, creatine kinase, total bilirubin, direct and indirect bilirubin, GGT, PT/INR, and alkaline phosphatase. A detailed history, including relevant information, such as review of ethanol, acetaminophen, recreational drug and supplement consumption, family history, occupational exposure, sexual history, travel history, history of contact with a jaundiced patient, surgery, blood transfusion, history of liver or allergic disease, and work exposure, should be collected. Further testing for acute hepatitis A, B, or C infection and liver imaging (e.g., biliary tract) may be warranted. All cases confirmed on repeat testing as meeting the laboratory criteria defined above, with no other cause for liver function test (LFT) abnormalities identified at the time should be considered potential Hy's Law cases irrespective of availability of all the results of the investigations performed to determine etiology of the abnormal LFTs. Such potential Hy's Law cases should be reported as SAEs.

Version: Amendment 4 Date: 31 Mar 2020

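### The 7-day hepatic DLT exemption has no carve-out for concurrent ALT/AST and bilirubin elevation, so a Grade ≥ 3 potential Hy's Law case that recovers adds nothing to the DLT count

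*Combined protocol and SAP*

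**What the plan says.** The DLT list in section 3.7.1 treats liver tests in three items, and the synopsis (section 2.1) repeats them.

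- **Exemption.** Under the general Grade ≥ 3 item, bilirubin or transaminase changes are excluded if they are "elevations that return to ≤ Grade 1 (if normal at study entry) or ≤ baseline values within 7 days of interrupting study drug".
- **DLT bullet.** The matching bullet counts "Grade ≥ 3 total bilirubin or hepatic transaminase (ALT or AST) elevations that do not return to ≤ Grade 1" (or to baseline, as applicable) within the same 7 days. The synopsis has the same condition: "elevations that do not return to ≤ Grade 1 (if normal at study entry) or ≤ baseline values".
- **Gilbert's item.** A separate threshold applies to patients with that condition "with Grade 2 bilirubin at baseline, total bilirubin ≥ 10 x upper limit of normal".

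Section 5.5.1 defines a potential Hy's Law case for a patient with normal baseline values as "AST or ALT ≥ 3 x ULN concurrent with a total bilirubin ≥ 2 x ULN", with no hemolysis and alkaline phosphatase at most 2 × ULN or not available. "All cases confirmed on repeat testing as meeting the laboratory criteria defined above, with no other cause for liver function test (LFT) abnormalities identified" are to be treated as potential Hy's Law cases and reported as SAEs. That section does not mention DLTs or escalation, and the DLT list does not mention section 5.5.1.

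Under the escalation rules in section 3.7.1, no DLT in three patients leads to the next dose level, one DLT expands the cohort to at most six, and a second DLT sets the MTD one level lower (45 mg if this happens at 60 mg).

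**The concern.** Exempting an isolated, reversible enzyme rise is a legitimate choice. Concurrent transaminase and bilirubin elevation without another cause is a different kind of event, and the protocol says so itself: section 5.5.1 always treats it as an important medical event. The DLT definition nevertheless gives it the same 7-day exemption.

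The exemption immediately before it, for amylase, lipase and creatine phosphokinase, applies only if the abnormality is asymptomatic and "without other laboratory evidence suggestive of pancreatitis, rhabdomyolysis, or other major organ dysfunction". The hepatic exemption has no comparable condition.

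DLTs are the primary endpoint and drive escalation, and every planned Stage 1 dose (60 mg upward) exceeds the 45 mg MTD of the previous study. A case of this kind that recovers would leave the primary endpoint at zero, and the written rule would point newly recruited patients to a higher dose.

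**Working it through.** The plan gives no figure to reproduce. The check is a trace of the rules, followed by an illustration of size.

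**Trace.** Take three patients at one dose level with no other DLT. One has a related Grade ≥ 3 elevation in Days 1–28 that meets section 5.5.1, is confirmed on repeat with no other cause, and recovers within 7 days of interruption.

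1. The hepatic DLT bullet does not apply, because the elevation recovered.
2. The general Grade ≥ 3 item does not apply, because the exemption removes it.
3. The count is 0/3, and the written rule escalates. It would still read 0/3 with two or three such cases.
4. If the case counted, one would read 1/3 and expand the cohort. Two would read 2/3 and set the MTD one level lower.

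**Size.** Let *h* be the per-patient rate of such cases and *o* the rate of other DLTs. The documents give neither. Both are assumed, and treated as independent.

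- Combined rate: q = 1 − (1 − o)(1 − h)
- Chance of escalating past a level: (1 − q)³ + 3q(1 − q)⁵
- Chance of at least one case in three patients: 1 − (1 − h)³

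Example, o = 10% and h = 1%: 1 − q = 0.90 × 0.99 = 0.891, so 0.891³ + 3 × 0.109 × 0.891⁵ = 0.707 + 0.184 = 0.891. Under the current definition these cases do not count, so h is set to 0: 0.9³ + 3 × 0.1 × 0.9⁵ = 0.729 + 0.177 = 0.906.

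| h | At least one case in 3 | P(escalate), o = 10% | P(escalate), o = 20% |
|---|---|---|---|
| not counted (current) | – | 0.906 | 0.709 |
| 0.5% | 1.5% | 0.899 | 0.700 |
| 1% | 3.0% | 0.891 | 0.691 |
| 2% | 5.9% | 0.875 | 0.674 |

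Given one case and no other DLT in the first three, escalation after the change needs no DLT in three more patients, (1 − q)³. For h = 1% that is 0.707 (o = 10%) or 0.497 (o = 20%); for h = 2%, 0.686 or 0.482. The current count alone would permit escalation without that further look.

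**How large h might be.** The Risk/Benefit Analysis section reports 47 patients in the previous study, at 2–65 mg. It names no hepatic DLT, and no liver event among the most frequent attributed AEs or the most common related Grade 3 AEs. It does not state the number of concurrent elevations. If that number were zero (assumed), the one-sided 95% upper limit would be 1 − 0.05^(1/47) = 6.2%. This study plans levels above 65 mg (75, 90 and 105 mg).

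**Detection.** Scheduled chemistry relevant to Cycle 1 is on Day 1 (Table 1) and within 48 hours before Cycle 2 (section 4.9.1). Without unscheduled tests, few transient cases would be seen.

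**The case against.** The strongest reply is that a 0/3 count does not escalate by itself. Sections 3.7.1 and 7.1 give the decision to the Cohort Review Committee, which reviews other safety and PK data as well as DLTs, and the sponsor may halt or modify escalation. A confirmed case is an SAE notified within 24 hours (section 5.12.1), so in a cohort of three the decision-makers would know of it. The committee's charter is not among the documents and may contain a hepatic rule.

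Most of this stands. A reader might infer that one such case makes escalation certain, but the documents do not support that: they leave room to stop, and the conditional figures above describe the count, not what the committee would do. What remains is that the protocol states no hepatic trigger, and that discretion leaves the primary endpoint at zero. The retreatment criteria in section 4.9.1 protect the affected patient but do not alter the cohort count.

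A reader might also infer that cases below Grade 3 are missed. That depends on CTCAE cut-offs that the documents do not give, so it is not claimed.

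The reply that such cases are probably rare is also fair. It limits the size of the effect, but does not explain why a detected and confirmed case should count for nothing.

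**Conclusion.** The gap is real and narrow. As written, a related Grade ≥ 3 hepatic elevation in Days 1–28 that also meets the protocol's own potential Hy's Law criteria is not a DLT if it recovers within 7 days of interrupting drug. The written 3+3 rule then lets a cohort with no other DLT escalate, subject only to discretion for which the protocol states no hepatic trigger.

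The average effect is small: a fall of 0.7 to 3.1 percentage points in the chance of escalating past a level if other DLTs run at 10% and h lies between 0.5% and 2%. The rule would operate rarely. These sizes rest on assumed rates; the gap itself rests only on the text. The change is still worth making, because the event is serious, the doses exceed the previous MTD and the amendment is short.

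**What to change.** Make two edits, each in both section 3.7.1 and the synopsis.

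1. To the 7-day hepatic exemption, add that it does not cover elevations accompanied by concurrent AST or ALT ≥ 3 × ULN and total bilirubin ≥ 2 × ULN (alkaline phosphatase ≤ 2 × ULN or unavailable, no hemolysis), confirmed on repeat testing and with no other cause identified.
2. To the hepatic DLT bullet, add Grade ≥ 3 elevations meeting that concurrent criterion, whether or not they recover.

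For raised baselines, use the section 5.5.1 transaminase threshold. With entry capped at 2.5 × ULN, it works out at 3 to 5 × ULN. For bilirubin, require a rise of at least 1 × ULN from baseline and a value of at least 2 × ULN. With entry capped at 1.5 × ULN, that means more than 2 and up to 2.5 × ULN.

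Do not carry over the section 5.5.1 bilirubin alternative of 3 "x the lower limit of normal (whichever is smaller"). In ULN units it equals 3 ÷ (ULN/LLN): 1.5, 1.0 or 0.75 for assumed ratios of 2, 3 or 4. At a ratio of 3 or more, a patient entering with bilirubin above normal already meets it.

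Patients under the Gilbert's item follow that item. Nothing changes for isolated reversible elevations or for cases below Grade 3.

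No new data are needed, since section 5.5.1 already requires the tests and work-up. The costs are a possible wait for confirmation and work-up before a cohort decision, an occasional expansion from three to six patients or a stop one level earlier, and application of the DLT termination rule to the patient unless the Investigator and medical monitor agree to continue, as section 3.7.1 allows.
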